5.5 Concomitant Medications/Vaccinations (Allowed & Prohibited)

Medications or vaccinations specifically prohibited in the exclusion criteria are not allowed during the ongoing trial. If there is a clinical indication for any medication or vaccination specifically prohibited during the trial, discontinuation from trial therapy or vaccination may be required. The investigator should discuss any questions regarding this with the Sponsor Clinical Director. The final decision on any supportive therapy or vaccination rests with the investigator and/or the subject's primary physician. However, the decision to continue the subject on trial therapy or vaccination schedule requires the mutual agreement of the investigator, the Sponsor and the subject.

5.5.1 Acceptable Concomitant Medications

- All treatments that the investigator considers necessary for a subject's welfare may be administered at the discretion of the investigator in keeping with the community standards of medical care. All concomitant medication will be recorded on the CRF including all prescription, over-the-counter (OTC), herbal supplements, and IV medications and fluids. If changes occur during the trial period, documentation of drug dosage, frequency, route, and date may also be included on the CRF.

- All medications received within 30 days before the first dose of trial treatment and 30 days after the last dose of trial treatment should be recorded. Concomitant medications administered after 30 days after the last dose of trial treatment should be recorded for SAEs and ECIs as defined in Section 7.2.
- Concurrent anti-cancer therapy with agents other than those assigned for each treatment arm (i.e., axitinib plus pembrolizumab or sunitinib) is not allowed. Medications intended solely for supportive care (i.e., antiemetics, analgesics, megestrol acetate for anorexia) are allowed.

5.5.1.1 Caution Use of Inhibitors and Inducers of CYP Enzymes (Axitinib)

In vitro studies with human liver microsomes and recombinant CYP enzymes indicate that axitinib metabolism is primarily mediated by the CYP3A4/5, and to a lesser extent by CYP1A2, CYP2C19, and UGT1A1.

The concomitant use of strong CYP3A4/5 inhibitors (e.g., ketoconazole, itraconazole, clarithromycin, atazanavir, indinavir, nefazodone, nelfinavir, ritonavir, saquinavir, telithromycin, and voriconazole) should be avoided. Grapefruit or grapefruit juice may also increase axitinib plasma concentrations and should be avoided. Selection of an alternate concomitant medication with no or minimal CYP3A4/5 inhibition potential is recommended. Although axitinib dose adjustment has not been studied in patients receiving strong CYP3A4/5 inhibitors, if a strong CYP3A4/5 inhibitor must be co-administered, a dose decrease of axitinib by approximately half is recommended, as this dose reduction is predicted to adjust the axitinib area under the plasma concentration vs. time curve (AUC) to the range observed without inhibitors. The subsequent doses can be modified based on individual safety and tolerability. If co-administration of the strong inhibitor is discontinued, the axitinib dose should be returned (after 3-5 half-lives of the inhibitor) to that used prior to initiation of the strong CYP3A4/5 inhibitor.

Co-administration of axitinib with strong CYP3A4/5 inducers (e.g., rifampin, dexamethasone, phenytoin, carbamazepine, rifabutin, rifapentin, phenobarbital, and St. John's wort) should be avoided. Selection of concomitant medication with no or minimal CYP3A4/5 induction potential is recommended. Moderate CYP3A4/5 inducers (e.g., bosentan, efavirenz, etravirine, modafinil, and nafcillin) may also reduce the plasma exposure of axitinib and should be avoided if possible.

5.5.1.2 Caution Use of Inhibitors and Inducers of CYP Enzymes (Sunitinib)

In vitro studies indicated that sunitinib does not induce or inhibit major CYP enzymes. The *in vitro* studies in human liver microsomes and hepatocytes of the activity of CYP isoforms CYP1A2, CYP2A6, CYP2B6, CYP2C8, CYP2C9, CYP2C19, CYP2D6, CYP2E1, CYP3A4/5, and CYP4A9/11 indicated that sunitinib and its primary active metabolite are unlikely to have any clinically relevant drug-drug interactions with drugs that may be metabolized by these enzymes.

Strong CYP3A4 inhibitors such as ketoconazole may **increase** sunitinib plasma concentrations. Selection of an alternate concomitant medication with no or minimal enzyme inhibition potential is recommended. Concurrent administration of SUTENT with the strong CYP3A4 inhibitor, ketoconazole, resulted in 49% and 51% increases in the combined

(sunitinib + primary active metabolite) C_{max} and $AUC_{0-\infty}$ values, respectively, after a single dose of SUTENT in healthy volunteers. Co-administration of SUTENT with strong inhibitors of the CYP3A4 family (e.g., ketoconazole, itraconazole, clarithromycin, atazanavir, indinavir, nefazodone, nelfinavir, ritonavir, saquinavir, telithromycin, voriconazole) may increase sunitinib concentrations. Grapefruit may also increase plasma concentrations of sunitinib. A dose reduction for SUTENT should be considered when it must be co-administered with strong CYP3A4 inhibitors.

CYP3A4 inducers such as rifampin may **decrease** sunitinib plasma concentrations. Selection of an alternate concomitant medication with no or minimal enzyme induction potential is recommended. Concurrent administration of SUTENT with the strong CYP3A4 inducer, rifampin, resulted in a 23% and 46% reduction in the combined (sunitinib + primary active metabolite) maximum concentration (C_{max}) and $AUC_{0-\infty}$ values, respectively, after a single dose of SUTENT in healthy volunteers. Co-administration of SUTENT with inducers of the CYP3A4 family (e.g., dexamethasone, phenytoin, carbamazepine, rifampin, rifabutin, rifapentin, phenobarbital, St. John's wort) may decrease sunitinib concentrations. St. John's wort may decrease sunitinib plasma concentrations unpredictably. Patients receiving SUTENT should not take St. John's wort concomitantly. A dose increase for SUTENT should be considered when it must be co-administered with CYP3A4 inducers.

The investigator should refer to the approved prescribing information for sunitinib (Sutent) for guidance on permitted medications and non-drug therapies [Sutent Package Insert, 2011].

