The study is using the label-recommended dose and schedule for RCC (50 mg QD 4 weeks on, 2 weeks off). Dose interruption and/or dose modification in 12.5-mg increments or decrements is recommended based on individual safety and tolerability, as per label recommendations. If 50 mg QD cannot be tolerated, the next dose level is 37.5 mg QD. Dose can be further reduced to 25 mg QD. Once toxicity has been alleviated, doses should be re-escalated stepwise to 37.5 mg and then 50 mg. Subjects requiring a dose below 25 mg QD should be permanently discontinued from study treatment. During each 6-week cycle, subjects will be off of treatment for 2 weeks. If an additional dose interruption for more than 2 weeks is required, the Sponsor should be consulted (Table 11).

Table 11 Dose Modification Guidelines for AEs Potentially Associated with Sunitinib Treatment

Toxicity	NCI CTCAE Grade	Sunitinib
Hypertension See Section 5.6.2 for monitoring/management of treatment-related hypertension.	SBP \leq 150 mm Hg and / or DBP \leq 100 mm Hg	Continue at the same dose level Antihypertensive treatment maybe initiated
	SBP >150 mm Hg but < 160 mm Hg and / or DBP >100 mm Hg but < 105 mm Hg	Continue at the same dose level, and institute new or additional antihypertensive medication if not on maximal antihypertensive treatment, or Reduce by 1 dose level if on maximal antihypertensive treatment.
	SBP >160 mm Hg and / or DBP > 105 mm Hg	Hold dose and adjust antihypertensive medication to achieve BP controlled to SBP \leq 150 mm Hg and DBP \leq 100 mm Hg. Resume at the same dose level or 1 level reduced. Note: If sunitinib dosing is temporarily interrupted, subjects receiving antihypertensive medications should be monitored closely for hypotension.
	Recurrent hypertensions following previous dose reduction	Repeat dose interruption and/or dose reduction by one lower dose level. Permanently discontinue if hypertension is severe and persistent despite antihypertensive treatment and dose interruption, or experience hypertensive crisis, transient or permanent neurological deficit related to uncontrolled hypertension.

Toxicity	NCI CTCAE Grade	Sunitinib
Proteinuria	Dipstick negative or 1+	Continue at the same dose level.
	If dipstick shows $\geq 2+$, perform 24-hour urine protein or UPC. Dosing may continue while waiting for test results	
	Urine protein < 3 g/24 hr or UPC < 3	Continue at the same dose level.

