All adverse events that occur after the consent form is signed but before treatment allocation/randomization must be reported by the investigator if they cause the subject to be excluded from the trial, or are the result of a protocol-specified intervention, including but not limited to washout or discontinuation of usual therapy, diet, placebo treatment or a procedure. From the time of treatment allocation/randomization through 30 days following cessation of treatment, all adverse events must be reported by the investigator. Such events will be recorded at each examination on the Adverse Event case report forms/worksheets. The reporting timeframe for adverse events meeting any serious criteria is described in section 7.2.3.1. The investigator will make every attempt to follow all subjects with non-serious adverse events for outcome.

Electronic reporting procedures can be found in the Electronic Data Capture (EDC) data entry guidelines. Paper reporting procedures can be found in the Investigator Trial File Binder (or equivalent).

7.2.1 Definition of an Overdose for This Protocol and Reporting of Overdose to the Sponsor

In this trial, an overdose is any dose exceeding 5 times the prescribed dose of pembrolizumab (200 mg), defined as any dose higher than 1000 mg. No specific information is available on the treatment of overdose of pembrolizumab. In the event of overdose, pembrolizumab should be discontinued and the subject should be observed closely for signs of toxicity. Appropriate supportive treatment should be provided if clinically indicated. Overdose for sunitinib and axitinib is any dose exceeding the prescribed maximum dose for each drug (i.e., 5 mg BID for axitinib unless dose escalation to 7 mg or 10 mg BID is permitted per Section 5.2.1.2.1. or 50 mg QD for sunitinib). There is no specific treatment for sunitinib or axitinib overdose. In the event of overdose, the dose should be interrupted and the subject should be observed closely for signs of toxicity. Appropriate supportive treatment should be provided if clinically indicated. The subject may resume study treatment at the discretion of the investigator (refer to axitinib and sunitinib labeling for more details).

If an adverse event(s) is associated with ("results from") the overdose of Sponsor's product or vaccine, the adverse event(s) is reported as a serious adverse event, even if no other seriousness criteria are met.

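### Section 5.5.1.2 contemplates a sunitinib increase with CYP3A4 inducers that, from 50 mg QD, Section 7.2.1 would class as an overdose

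*Combined protocol and SAP*

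**What the plan says.** Sunitinib is started at 50 mg QD, 4 weeks on and 2 weeks off (Sections 2.1 and 5.2, Table 5). Three sections bear on whether the dose may go higher.

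- **Section 5.5.1.2** recommends choosing a concomitant drug with little or no enzyme induction. For the case where that is not possible it adds: "A dose increase for SUTENT should be considered when it must be co-administered with CYP3A4 inducers". It gives no upper limit and does not refer to the overdose definition.
- **Section 7.2.1** states: "Overdose for sunitinib and axitinib is any dose exceeding the prescribed maximum dose for each drug". The maximum for axitinib is 5 mg BID, with a qualification, and the sunitinib figure follows in the same parenthesis: "unless dose escalation to 7 mg or 10 mg BID is permitted per Section 5.2.1.2.1. or 50 mg QD for sunitinib". On the action to take it says: "In the event of overdose, the dose should be interrupted and the subject should be observed closely for signs of toxicity". It then lets the subject resume at the investigator's discretion, and it requires all overdoses, with or without an adverse event, to be reported to the Sponsor within 24 hours.
- **Section 5.2.2.4** says: "Dose interruption and/or dose modification in 12.5-mg increments or decrements is recommended based on individual safety and tolerability". The levels it names are 50, 37.5 and 25 mg QD, and re-escalation after toxicity ends at 50 mg.

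**The concern.** A site treating a subject at the full sunitinib dose who must take a CYP3A4 inducer has two instructions that do not fit together. If it acts on Section 5.5.1.2 and raises the dose, Section 7.2.1 tells it to interrupt that dose and report an overdose.

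Two things are at stake. The first is subject safety: the site cannot tell from the protocol whether the higher dose is sanctioned or is an error to be corrected. The second is how control-arm safety data are read. Under Sections 7.2.1 and 7.2.3.2 an overdose without symptoms or abnormal laboratory results is an Event of Clinical Interest, and an adverse event associated with an overdose is reported as serious even if it meets no other seriousness criterion. Control-arm overdose and ECI counts, and possibly a few serious events, could then include dosing that the protocol itself suggested. The primary PFS and OS analyses do not depend on this.

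**Working it through.** The plan gives no statistical figure to reproduce here. The check sets the sections side by side and applies the protocol's own step size to its own threshold.

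**Inputs**
- Starting dose: 50 mg QD (Table 5).
- Step size: 12.5 mg (Section 5.2.2.4).
- Named levels: 50, 37.5 and 25 mg QD (Section 5.2.2.4).
- Overdose threshold: any dose above 50 mg QD (Section 7.2.1).

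**Step 1. One step up from each named level**

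| Dose before inducer | Dose after one step | Above 50 mg? |
|---|---|---|
| 25 mg | 25 + 12.5 = 37.5 mg | No |
| 37.5 mg | 37.5 + 12.5 = 50 mg | No |
| 50 mg | 50 + 12.5 = 62.5 mg | Yes, by 12.5/50 = 25% |

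Section 5.5.1.2 does not fix the size of the increase, but the last row does not depend on it: any increase from 50 mg is above 50 mg.

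**Step 2. Is there an exception?** Section 7.2.1 exempts axitinib at 7 or 10 mg BID where escalation is permitted. The sunitinib clause is only "or 50 mg QD for sunitinib", with nothing attached. The axitinib exception cites Section 5.2.1.2.1, which is not in the table of contents; axitinib escalation is described in Section 5.2.2.2. No comparable pointer leads from the sunitinib threshold to Section 5.5.1.2.

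**Step 3. Does another section supply a higher level?** Section 5.2.2.4 speaks of increments as well as decrements, but the only upward movement it describes is re-escalation to 37.5 and then 50 mg.

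**Step 4. Can the situation arise?** Exclusion 24 covers strong CYP3A4/5 inducers. The advice in Section 5.5.1.2 is not limited to strong inducers, and Section 5.5.1.1 itself recognises a class of moderate ones. The entry criteria therefore make the case less frequent without removing it.

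**Step 5. Do the reporting rules reach sunitinib?** Section 7.2.1 names it directly. Section 7.2 counts an active comparator provided by the Sponsor as Sponsor's product, and Table 21 lists sunitinib as supplied centrally by the Sponsor or locally.

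**Step 6. Scale.** No frequency of inducer use is given. With 861 subjects randomised 1:1 there are about 861/2 ≈ 430 on sunitinib, so each affected subject would add about 1/430 ≈ 0.23 percentage points to a control-arm incidence. This takes the safety population as close to all those randomised.

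**The case against.** The strongest reply is that the conflict is small and mostly avoidable. Section 5.5.1.2 recommends an alternative drug first and asks only that an increase be considered, so a site that considers it and declines has complied. A subject already reduced to 25 or 37.5 mg has room to go up. Section 7.2.1 calls for interruption, not permanent discontinuation. Strong inducers are excluded at entry. All of this stands and limits the point. None of it resolves the case of a subject at 50 mg QD whose dose is raised.

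One could also argue that the prescribed maximum means whatever the investigator prescribed. The parenthesis in Section 7.2.1 fixes it at 50 mg QD, so that reading fails. Section 5.5.1.2 also refers the investigator to the sunitinib prescribing information, but for permitted medications and non-drug therapies; that does not change the protocol's own threshold.

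A reader might infer three stronger criticisms from the same sections. The documents do not support them.

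- *That strong CYP3A4/5 inhibitors and inducers are flatly barred during treatment and yet given dosing advice.* Section 5.5 does say: "Medications or vaccinations specifically prohibited in the exclusion criteria are not allowed during the ongoing trial". It goes on to allow for a clinical need, treats discontinuation as possible rather than automatic, and lets the subject continue if investigator, Sponsor and subject agree. The end of Section 5.5.3 deals with long-term need for prohibited drugs. Sections 5.5.1.1 and 5.5.1.2 advise avoidance or an alternative first. What remains is loose cross-referencing: the list in Section 5.5.3 does not mention the strong CYP3A4/5 drugs named in exclusions 23 and 24.
- *That Section 5.5.1.1 gives an axitinib dose adjustment for inducers.* It does not. It gives one for strong inhibitors; for inducers it advises only avoidance.
- *That halving axitinib 5 mg gives 2.5 mg, which is not a level in Table 9.* The text reads: "a dose decrease of axitinib by approximately half is recommended". The instruction is approximate, and Table 9 has 3 mg and 2 mg on either side.

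**Conclusion.** The narrow inconsistency holds. For a subject on sunitinib 50 mg QD, an increase contemplated by Section 5.5.1.2 meets the overdose definition in Section 7.2.1, with interruption and a 24-hour report to follow, and no text reconciles the two.

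The conclusion rests on the wording alone: that 50 mg QD is the stated maximum, that sunitinib has no exception, and that the inducer advice is not confined to subjects below 50 mg. The number affected is unknown. It is probably small, because strong inducers are excluded at entry and an alternative drug is to be preferred. This is a wording defect with a bearing on safety and on control-arm overdose counts. It does not threaten the efficacy conclusions and is of low priority, but it is worth correcting because correction is cheap.

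**What to change.** Reconcile Section 5.5.1.2 with Sections 7.2.1 and 5.2.2.4, so that a sunitinib dose contemplated in one section is not an overdose in another. Which rule should apply is a decision for the sponsor's clinical team. In the same edit, correct the reference to Section 5.2.1.2.1 in Section 7.2.1.

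As a minor matter, align Sections 5.5.1.1 and 5.5.1.2 and the list in Section 5.5.3 with exclusions 23 and 24, the opening of Section 5.5 and the closing paragraph of Section 5.5.3, so that use of strong CYP3A4/5 inhibitors and inducers during treatment is described in one consistent way.

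The cost is wording in a handful of subsections. Sample size, data collection and the planned analyses do not change.

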5.5.1.3 Hematopoietic Growth Factors

Primary prophylactic use of granulocyte-colony stimulating factors may be used to treat treatment emergent neutropenia as indicated by the current American Society of Clinical Oncology guidelines [55]. The use of hematopoietic growth factors is at the discretion of the treating physician in line with local guidelines. Subjects who enter the study on stable doses of erythropoietin or darbepoietin may continue this treatment, and subjects may start either drug during the study at the discretion of the treating physician.

5.5.2 Concomitant Surgery

Subjects can receive surgical procedures during the study treatment period for indications other than treating RCC.

5.5.2.1 Axitinib

No formal studies of the effect of axitinib on wound healing have been conducted; however, caution is advised based on the mechanism of action. If a major surgery or an interventional procedure (e.g., endoscopy) is required, treatment with axitinib must be interrupted at least 24 hours before the procedure and subject's BP should be monitored closely for hypotension. Subject may resume axitinib 7 days after minor surgery and 2 to 3 weeks after major surgery, provided that the wound has completely healed and there are no wound healing complications (e.g., delayed healing, wound infection or fistula).

5.5.2.2 Pembrolizumab

Dosing interruptions are permitted in the case of surgical events such as elective surgery. Subjects should be placed back on study therapy within 3 weeks of the scheduled interruption, unless otherwise discussed with the Sponsor. The reason for the interruption should be documented.

5.5.2.3 Sunitinib

Cases of impaired wound healing have been reported during sunitinib therapy. Temporary interruption of sunitinib therapy is recommended for precautionary reasons in patients undergoing major surgical procedures. There is limited clinical experience regarding the timing of re-initiation of therapy following major surgical intervention. Therefore, the decision to resume sunitinib therapy following a major surgical intervention should be based upon clinical judgment of recovery from surgery [refer to the Sutent Label for details].

5.5.3 Prohibited Concomitant Medications

Subjects are prohibited from receiving the following therapies during the study treatment period (including re-treatment for post-complete response relapse) of this trial:

- Any anti-cancer therapy not assigned per protocol (e.g., systemic treatment, surgery, radiation).

Note: Radiation therapy to a symptomatic solitary lesion or to the brain may be considered an exception on a case-by-case basis after consultation with Sponsor. The radiation treatment field may not include a target or measurable lesion by RECIST 1.1.

- Investigational agents other than those specified in this protocol (i.e., pembrolizumab, axitinib or sunitinib based on what is assigned)
- Live vaccines within 30 days prior to the first dose of pembrolizumab and through 30 days following the last dose of pembrolizumab. Examples of live vaccines include, but are not limited to, the following: measles, mumps, rubella, chickenpox, yellow fever, rabies, Bacillus Calmette-Guerin (BCG), and oral typhoid vaccine. Seasonal influenza vaccines for injection are generally killed virus vaccines and are allowed; however intranasal influenza vaccines (e.g., FluMist®) are live attenuated vaccines, and are not allowed.

Note: If precluded by local regulations, live vaccines should not be given for 120 days after the last dose of pembrolizumab is administered.

- Drugs with proarrhythmic potential: Concomitant treatment with a drug having known proarrhythmic risks (terfenadine, quinidine, procainamide, disopyramide, sotalol, probucol, bepridil, haloperidol, risperidone, indapamide and flecainide) is not permitted during treatment with sunitinib.

The following applies exclusively to subjects being treated with pembrolizumab plus axitinib:

- Prolonged therapy with systemic glucocorticoids for any purpose other than to modulate symptoms from an AE, SAE, or ECI or for use as a pre-medication for chemotherapy or in participants with a known history of an IV contrast allergy administered as part of computed tomography (CT) radiography. Brief, limited use of systemic corticosteroids (≤ 7 days) is permitted where such use is considered standard of care (e.g., for COPD exacerbation).

Replacement doses of steroids (for example, prednisone 5 to 7.5 mg daily) are permitted while on study, as is the use of local steroids.

Subjects who, in the assessment by the investigator, require additional anti-cancer treatments will be discontinued from study treatment and continue on survival follow-up. Subjects who, in the assessment by the investigator, require any other prohibited medications for the assigned study treatment for long-term clinical management should be discontinued from trial treatment but continue on disease assessments and survival follow-up. Subjects may receive other medications that the investigator deems to be medically necessary.

